9.2. Sample Size Determination

Approximately 250 participants will be randomized to study treatments (LY3209590 Algorithm 1 and insulin degludec) such that approximately 125 participants will be randomized to each treatment. Assuming a 20% dropout rate, approximately 200 participants will complete the study (approximately 100 participants per treatment group).

The 200 participants who complete the treatment will provide more than 80% statistical power to demonstrate the non-inferiority in the change in HbA1c from baseline to 26 weeks for LY3209590 Algorithm 1 versus insulin degludec, based on the following assumptions:

- True mean difference = 0%
- SD of 1.1%
- NIM of 0.4%
- Using 2-sided alpha level of 0.1

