5.11. FGM Analysis

5.11.1. General Consideration

The FGM system will be offered to all participants meeting study entry criteria except for reporting of screening clinical laboratory assessments in Study I8H-MC-BDCL (BDCL). Participants will undergo 3 FGM sessions using the LibrePro System (Abbott) in the 14-day period prior to randomization, Visit 15, and Visit 20. Patients will remain blinded to these assessments until the study is completed.

All patients who are randomized to either LY3209590 Algorithm 1 or insulin degludec receive at least 1 dose of study treatment, and have FGM data from baseline and at least 1 postbaseline collection period will be included in the analyses. The data collected after permanent discontinuation of the IP will be censored. There will be no multiplicity adjustment. Additional analysis may be conducted to compare between the LY3209590 (by pooling LY3209590 Algorithm 1 and LY3209590 Algorithm 2) and insulin degludec if deemed necessary.

According to the 2020 American Diabetes Association standard of medical care in diabetes, the FGM data will be included in the analysis only if at least 70% of the total measures in the analysis period are obtained (defined as a valid FGM period). For example, the 24-hour period will have 96 measures and the minimum number of measures will be 68. All the FGM derivations are based on the data from valid FGM period unless otherwise specified.

The FGM variables will be derived for each FGM day when the analysis data meeting the above requirement. The derived variables for a visit will be based on the daily FGM variables within the given visit.

Summary statistics will include the number of observations, mean, median, maximum, minimum, and SD for all continuous measures. For categorical measures, the number of observations, proportion, and frequency will be included in summary statistics. All analyses will be performed by visit and treatment.

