5.11.2. FGM Variable and Analysis

The continuous variables derived from FGM will be summarized and compared between treatment groups by visit using MMRM model. The model will include the treatment, HbA1c stratum (<8.5% or ≥8.5%), baseline value of the dependent variable, visit, and treatment by visit interaction. The raw mean and LS mean difference between treatment groups will be summarized.

For the between-day and within-day glucose variability, the variable will take log-transformation before performing the MMRM analysis.

The binary variables will be analyzed using a longitudinal logistic regression. In the longitudinal logistic regression model, the independent variables of treatment, baseline HbA1c value, baseline continuous variable corresponding to the binary dependent variable, visit, and treatment by visit interaction will be used.

For the hypoglycemia episodes defined by FGM, the analysis using a negative binomial model with the offset of log (exposure in year) will be performed. The model will include treatment and baseline HbA1c.

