5.11.2.1. Hypoglycemia

- Percentage and Duration (in minutes) of time per day where glucose values are within a hypoglycemic range (defined as <70 mg/dL [3.9 mmol/L]) during the nighttime period (defined as midnight to 0600 hours), the daytime period (defined as 0600 hours to 2400 hours) and a 24-hour period.
- Percentage and Duration (in minutes) of time per day where glucose values are within a hypoglycemic range (defined as <54 mg/dL [3.0 mmol/L]) during the nighttime period, the daytime and a 24-hour period.
- Percentage and Duration (in minutes) of time per day where glucose values are within a hypoglycemic range (defined as defined as <70 mg/dL [3.9 mmol/L] and ≥ 54 mg/dL [3.0 mmol/L]) during the nighttime period, the daytime period and a 24-hour period.
- Incidence of hypoglycemic episodes (defined as <70 mg/dL [3.9 mmol/L], or <54 mg/dL [3.0 mmol/L] or <70 mg/dL [3.9 mmol/L] and ≥ 54 mg/dL [3.0 mmol/L]) during the nighttime period, the daytime period and a 24-hour period.
- Rate of hypoglycemic episodes (defined as <70 mg/dL [3.9 mmol/L], or <54 mg/dL [3.0 mmol/L] or <70 mg/dL [3.9 mmol/L] and ≥ 54 mg/dL [3.0 mmol/L]) during the nighttime period, the daytime period and a 24-hour period.
- Duration (in minutes) of each individual hypoglycemic episode (defined as <70 mg/dL [3.9 mmol/L], or <54 mg/dL [3.0 mmol/L] or <70 mg/dL [3.9 mmol/L] and ≥ 54 mg/dL [3.0 mmol/L] for at least 30 minutes).

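### The negative binomial model for FGM hypoglycemic episodes leaves out the patient's own FGM baseline, which the other two FGM models include: a minor efficiency and consistency gap on an exploratory endpoint

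*SAP*

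**What the plan says.** SAP 5.11.2 sets out three models for FGM outcomes.

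- **Continuous variables:** a repeated-measures model with treatment, HbA1c stratum, and "baseline value of the dependent variable, visit, and treatment by visit interaction".
- **Binary variables:** a longitudinal logistic model whose terms include baseline HbA1c and the "baseline continuous variable corresponding to the binary dependent variable".
- **Hypoglycemic episodes:** "the analysis using a negative binomial model with the offset of log (exposure in year) will be performed". The next sentence reads: "The model will include treatment and baseline HbA1c".

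SAP 5.11.2.1 lists episode rates at several glucose thresholds, for night, day and 24 hours. Sensors are worn "in the 14-day period prior to randomization, Visit 15, and Visit 20", so the first session precedes treatment. Under SAP 5.11.1, patients on Algorithm 1 or degludec who took a dose and "have FGM data from baseline and at least 1 postbaseline collection period will be included in the analyses". Neither document explains why the episode model has no FGM baseline, and neither adds one elsewhere.

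**The concern.** A patient's own earlier value is usually the most useful covariate for a repeated measure. Baseline HbA1c reflects average glycemia and is only an indirect marker of sensor-detected lows. Two of the three FGM models use the matching baseline and the third does not, although the data come from the same session in the same patients.

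What is at stake is precision. If baseline episodes predict later ones, omitting them widens the interval for the episode rate ratio and leaves chance baseline imbalance in episodes uncorrected. The endpoint is of some interest because the trial is open-label and diary hypoglycemia is entered by patients, whereas FGM is recorded by a sensor whose output patients do not see until the study ends.

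**Working it through.** **1. The plan's own figure.** The only power statement (Protocol 9.2) concerns HbA1c: more than 80% with about 100 completers per arm, SD 1.1, margin 0.4, true difference 0, two-sided alpha 0.1. The standard error is 1.1 × √(2/100) = 0.1556. Then 0.4/0.1556 − 1.645 = 0.93, and Φ(0.93) is about 82%, so the statement reproduces. Randomizing 200/(1 − 0.20) = 250 also agrees. No corresponding figure exists for FGM episodes. The one input carried forward is 100 patients per arm.

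**2. The three models side by side.**

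| FGM outcome | Own FGM baseline in model? | HbA1c term? |
|---|---|---|
| Continuous | Yes | Yes (stratum) |
| Binary | Yes (matching continuous variable) | Yes |
| Episode rate | No | Yes |

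**3. What baseline is available.** SAP 5.11.1 guarantees baseline FGM data, which is not the same as a baseline episode: many counts may be zero. It also does not guarantee a valid baseline for every period of day. The SAP's example gives 96 readings per 24 hours, of which 68 are needed. Midnight to 0600 holds 96 × 6/24 = 24 of them. A day with no night readings still has 96 − 24 = 72, which passes the 24-hour test. A nighttime baseline can therefore be missing in an included patient.

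**4. Size.** Episode rates, between-patient spread and correlation are all assumptions. Counts were simulated with log-normal patient effects, 100 per arm, and fitted by negative binomial regression with and without a count-based baseline term. The measure is the reduction in variance of the log rate ratio.

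With a post-baseline mean of 2 episodes and correlation of 0.3 to 0.7:

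| Baseline mean episodes | Variance reduction |
|---|---|
| 0.1 | about 0-1% |
| 0.5 | 0-7% |
| 2 | 2-16% |

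With log-scale patient SD 1.0 and the baseline mean at half the post-baseline mean, median standard-error ratios (adjusted over unadjusted) convert as 1 − ratio²:

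- post-baseline mean 1, correlation 0.3: 1 − 0.995² = 1%
- post-baseline mean 2, correlation 0.5: 1 − 0.967² = 6%
- post-baseline mean 4, correlation 0.7: 1 − 0.898² = 19%

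The top of the range is thus roughly 15-20%. On the log scale the interval narrows by 1 − √0.85 = 8% to 1 − √0.80 = 11%.

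**5. Sensitivity.** A third set used a wider patient spread (log-rate variance 1.5) and measured the scatter of the estimates over 300 simulated trials. It gave reductions of 2% to 45% for correlations of 0.3 to 0.7, including 2-19% at a baseline mean of 0.1. These figures are noisy. In the most favorable cell the variance ratio was 0.555 from the standard deviation but 0.750 from the interquartile range, that is, a reduction of 45% or 25%. They show that the upper end depends on the assumed spread, and they are not used as the headline.

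**6. If baseline is uninformative.** At zero correlation the variance ratio in that third set was 0.96 to 1.01, no different from 1 within simulation noise.

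**The case against.** The strongest reply is that nothing here is wrong. A randomized comparison adjusted for treatment and baseline HbA1c is valid, and the choice of further covariates is a preference. FGM outcomes are exploratory, carry no multiplicity adjustment, and support no power claim or decision rule. Time below each threshold is already analyzed with its own baseline, so a baseline-adjusted, sensor-based view of hypoglycemia is planned anyway. All of this stands, and it sets the priority.

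The gain may also be close to nil. Baseline FGM is recorded before any study insulin, in patients with screening HbA1c 7.0-9.5% and recent insulin or sulfonylurea use excluded (Protocol 5.1, 5.2). Protocol 6.1.2.2 describes the allowed oral drugs as non-secretagogues. SAP Appendix 1 expects even patient-reported hypoglycemia to be sparse in this population. Later episodes follow titration to a fasting target, so baseline may predict them weakly. This too stands, most of all for episodes below 54 mg/dL or at night.

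The form of the covariate matters as well. If the count plus 0.5 is divided by wear time and logged, patients with no episodes differ only by how long they wore the sensor. That is a reason to choose the form with care. It does not justify having no baseline term.

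Two stronger readings are tempting. A reader might infer that the episode rate ratio is biased; randomization rules that out. A reader might also infer a substantial loss of precision in every case; the documents supply none of the quantities needed to show one.

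**Conclusion.** The omission is real, unexplained, and out of line with the two neighboring models. It is a minor point of efficiency and consistency on an exploratory endpoint. The primary HbA1c analysis is unaffected.

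Under the stated assumptions the avoidable variance runs from about 0% (rare baseline episodes) to roughly 15-20% (frequent baseline episodes, correlation 0.7, log-scale patient SD around 1.0). A wider patient spread could raise the upper end. The useful case is most likely episodes below 70 mg/dL over 24 hours. The direction depends on baseline episodes predicting later ones; if they do not, adjustment costs nothing material.

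**What to change.** In SAP 5.11.2, add to the negative binomial model, alongside baseline HbA1c, the patient's baseline FGM hypoglycemia for the same threshold and period of day. The form should handle zeros and should not vary with wear time alone. Two candidates are:

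- **Baseline percentage of time below the same threshold.** It is already derived for the repeated-measures analysis. It can be above zero in a patient without an episode, because an episode requires at least 30 minutes (SAP 5.11.3.2). The gains above were computed for count-based terms, so its own gain is not quantified here.
- **Log of (baseline episode rate plus a fixed constant)**, with the constant and the time unit stated in advance. All patients with no episodes then share one value.

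State one form before the final data lock. For a patient without a valid baseline in a given period of day, use the 24-hour baseline value, so that no one leaves the analysis.

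The cost is one covariate and one fallback rule in the SAP. No new data, visits or patients are needed.

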5.11.2.1. Hypoglycemia

- Percentage and Duration (in minutes) of time per day where glucose values are within a hypoglycemic range (defined as <70 mg/dL [3.9 mmol/L]) during the nighttime period (defined as midnight to 0600 hours), the daytime period (defined as 0600 hours to 2400 hours) and a 24-hour period.
- Percentage and Duration (in minutes) of time per day where glucose values are within a hypoglycemic range (defined as <54 mg/dL [3.0 mmol/L]) during the nighttime period, the daytime and a 24-hour period.
- Percentage and Duration (in minutes) of time per day where glucose values are within a hypoglycemic range (defined as defined as <70 mg/dL [3.9 mmol/L] and ≥ 54 mg/dL [3.0 mmol/L]) during the nighttime period, the daytime period and a 24-hour period.
- Incidence of hypoglycemic episodes (defined as <70 mg/dL [3.9 mmol/L], or <54 mg/dL [3.0 mmol/L] or <70 mg/dL [3.9 mmol/L] and ≥ 54 mg/dL [3.0 mmol/L]) during the nighttime period, the daytime period and a 24-hour period.
- Rate of hypoglycemic episodes (defined as <70 mg/dL [3.9 mmol/L], or <54 mg/dL [3.0 mmol/L] or <70 mg/dL [3.9 mmol/L] and ≥ 54 mg/dL [3.0 mmol/L]) during the nighttime period, the daytime period and a 24-hour period.
- Duration (in minutes) of each individual hypoglycemic episode (defined as <70 mg/dL [3.9 mmol/L], or <54 mg/dL [3.0 mmol/L] or <70 mg/dL [3.9 mmol/L] and ≥ 54 mg/dL [3.0 mmol/L] for at least 30 minutes).

5.11.2.2. Hyperglycemia

- Percentage and Duration (in minutes) of time per day glucose values are within a hyperglycemic range (defined as >180 mg/dL [10.0 mmol/L] and ≤ 250 mg/dL [13.9 mmol/L]) during the nighttime period, the daytime period and a 24-hour period.
- Percentage and Duration (in minutes) of time per day glucose values are within a hyperglycemic range (defined as >250 mg/dL [13.9 mmol/L] during the nighttime period, the daytime period and a 24-hour period.

5.11.2.3. Normal Range

Percentage and Duration (in minutes) of time per day glucose values are within a normal glycemia range (defined as between 70 mg/dL and 180 mg/dL [3.9 and 10.0 mmol/L]) inclusive during the nighttime period, the daytime period and a 24-hour period.

5.11.2.4. Glycemic Variability

- Low Blood Glucose Index (LBGI) during the nighttime period and a 24-hour period.
- High Blood Glucose Index (HBGI) during the nighttime period and a 24-hour period.
- Combined blood glucose risk index (BGRI derived as LBGI + HBGI) during the nighttime period and a 24-hour period.
- Within-day and between-day glucose coefficient of variation (CV) during the nighttime period and a 24-hour period.
- Within-day and between-day glucose coefficient of variation (CV) $\leq 36\%$ during the nighttime period and a 24-hour period.
- Within-day and between-day glucose SD during the nighttime period and a 24-hour period.
- Mean of daily differences (MODD) during the nighttime period and a 24-hour period.

5.11.2.5. Ambulatory Glucose Profile

The ambulatory glucose profile (AGP) during the 24-hour period will be generated with interquartile ranges, at treatment-group level by visit (baseline, Week 12 and Week 26), based upon the observed FGM measures.

5.11.2.6. FGM Targets of Glycemic Control

According to the guidance (Battelino 2019), the following FGM targets of glycemic control will also be derived during a 24-hour period.

- The percentage of time within a normal glycemia range (defined as between 70 mg/dL and 180 mg/dL [3.9 and 10.0 mmol/L]) $>70\%$
- The percentage of time within a hypoglycemic range (defined as defined as <70 mg/dL [3.9 mmol/L]) $<4\%$
- The percentage of time within a hypoglycemic range (defined as defined as <54 mg/dL [3.0 mmol/L]) $<1\%$
- The percentage of time within a hyperglycemic range (defined as >180 mg/dL [10.0 mmol/L]) $<25\%$
- The percentage of time within a hyperglycemic range (defined as >250 mg/dL [13.9 mmol/L]) $<5\%$

5.11.3. Definition of Variables

In this section, we define the derived variables that are used for the analysis in Section 5.11.2 and some additional variables that may be used for exploratory analyses.

5.11.3.1. Glucose in Target Ranges, Hypoglycemia or Hyperglycemia

The percentage of time within a glucose range (target, hypoglycemia or hyperglycemia ranges) will be calculated as the number of observations within the specified range divided by the number of observations in the time interval (for example, 24-hour period). The duration (in minutes) within the glucose range will then be calculated as the percentage of time within the glucose range times the length of the period (24 hour, 18 hour, and 6 hour, for the periods of 24 hour, daytime or nighttime, respectively).

5.11.3.2. Hypoglycemic Episode

The FGM-determined hypoglycemic episode is defined as glucose <54 mg/dL (or ≤ 70 mg/dL) for at least 30 minutes.

The duration of each episode will be calculated using the time difference between the 2 time points before the incidence starts and after the incidence ends.

The average duration will be calculated by dividing the sum of the duration of individual episodes during the given visit by the number of episodes.

The FGM-determined nighttime hypoglycemic episode is defined as hypoglycemic episodes that occur between 2400 hours and 0600 hours. To calculate the duration of nighttime hypoglycemic episode, the end date/time will be the end date/time when the patient passes outside the hypoglycemic range even if it is outside the interval of 2400 hours and 0600 hours.

5.11.3.3. Glycemic Variability

Glycemic variability will be evaluated using the notation below:

i represents a time point within a time period (a 24-hour period, daytime or nighttime)

n represents the number of time points within the time period

k represents a day within a visit

m represents number of days FGM is performed at a visit

BG_{*k,i*} represents the glucose value at time point *i* on day *k* unless otherwise specified.

- Within-Day Variability

For variables assessing within-day variability, first determine the variability within each day, then average across days within a visit.

Within-day glucose SD (Rodbard 2009):

$$SD = \frac{1}{m} \sum_{k=1}^m SD_k = \frac{1}{m} \sum_{k=1}^m \sqrt{\frac{\sum_{i=1}^n (BG_{k,i} - \frac{\sum_{i=1}^n BG_{k,i}}{n})^2}{n-1}}$$

Within-day glucose CV (Clarke and Kovatchev 2009):

$$CV = \frac{1}{m} \sum_{k=1}^m CV_k = \frac{1}{m} \sum_{k=1}^m \frac{SD_k}{\frac{\sum_{i=1}^n BG_{k,i}}{n}} \times 100$$

The LBGI, HBGI, and BGRI will be calculated using the standard formulas.

The LBGI has been developed to quantitate both frequency and severity of hypoglycemia. The LBGI has been validated as a predictor of severe hypoglycemia, which is an SAE and could result in coma or death if unrecognized and untreated. The HBGI quantifies both frequency and severity of hyperglycemia and has been related to HbA1c and risk for hyperglycemia (Kovatchev et al. 2006). Additionally, both the LBGI and HBGI have a high sensitivity to changes in glycemic profiles and control (Kovatchev et al. 2006). LBGI is a non-negative number that increases as the number of low readings increases. HBGI is a non-negative number that increases as the number of high readings increases.

The LBGI, HBGI, and BGRI will be derived for each day of a visit and then average across days within a visit. The calculations of LBGI, HBGI, and BGRI take the following steps:

Step 1: For each blood glucose (BG [mg/dL]) at the i^{th} time point, compute the following:

$$f(\text{BG}_i) = 1.509 \times [(\ln(\text{BG}_i))^{1.084} - 5.381]$$

This transforms the BG data using a nonlinear transformation that maps the BG range of 20 to 600 mg/dL to a symmetric interval of $(-\sqrt{10}, \sqrt{10})$

The center of the BG scale is 112.5 mg/dL and is mapped to 0

Step 2: Compute BG risk for each reading

$$rl(\text{BG}_i) = 10 \times f(\text{BG}_i)^2 \text{ if } f(\text{BG}) < 0; \text{ otherwise } rl(\text{BG}_i) = 0$$

$$rh(\text{BG}_i) = 10 \times f(\text{BG}_i)^2 \text{ if } f(\text{BG}) > 0; \text{ otherwise } rh(\text{BG}_i) = 0$$

Assign the risk of each BG value by applying the above quadratic risk function

Value range from 0 (achieved when BG = 112.5, the center) to 100

Left side of the parabola is risk of hypoglycemia, and the right side is risk of hyperglycemia

Step 3: Compute LBGI and HBGI

$$\text{LBGI} = \frac{1}{n} \sum_{i=1}^n rl(\text{BG}_i)$$

$$\text{HBGI} = \frac{1}{n} \sum_{i=1}^n rh(\text{BG}_i)$$

Step 4: Compute BGRI

$$\text{BGRI} = \text{LBGI} + \text{HBGI}$$

- Between-Day Variability

For variables assessing between-day variability, first determine the variability for each time point across days within a visit then average across all time points.

Between-day glucose SD (Rodbard 2009):

$$SD = \frac{1}{n} \sum_{i=1}^n SD_i = \frac{1}{n} \sum_{i=1}^n \sqrt{\frac{\sum_{k=1}^m (BG_{k,i} - \frac{\sum_{k=1}^m BG_{k,i}}{m})^2}{m-1}}$$

Between-day glucose CV (Kovatchev et al. 2009):

$$CV = \frac{1}{n} \sum_{i=1}^n CV_i = \frac{1}{n} \sum_{i=1}^n \frac{SD_i}{\left(\frac{\sum_{k=1}^m BG_{k,i}}{m} \right)} \times 100$$

Mean of daily differences (MODD): this parameter is calculated as the mean of absolute differences between glucose values at corresponding time points of consecutive days.

$$MODD = \frac{1}{m-1} \sum_{k=1}^{m-1} \frac{\sum_{i=1}^n |BG_{k+1,i} - BG_{k,i}|}{n}$$

5.12. Subgroup Analyses

The subgroups will be defined as:

- Body mass index (<30, ≥30)
- Baseline HbA1c (<8.5% and ≥8.5%)
- Baseline HbA1c (defined by baseline median)
- Concomitant medication (metformin alone and metformin in combination with other oral antidiabetic medications)

The outcome measures included in the subgroup analyses are:

- HbA1c and change in HbA1c from baseline to up to 26 weeks
- Documented hypoglycemia, non-nocturnal, and nocturnal hypoglycemia rates (glucose <70 mg/dL [3.9 mmol/L] and glucose ≥54 mg/dL [3.0 mmol/L]) during 0-26 weeks.

Analyses for HbA1c and its change will be performed examining the 3-way interaction of the primary treatment arms, visit and the subgroup variable using the same MMRM model described for the primary analysis. This model will include the same fixed effects given for the primary analysis model plus factors of subgroup, 2-way interaction of subgroup and treatment, 2-way interaction of subgroup and visit, and 3-way interaction of treatment, visit, and the subgroup.

The hypoglycemia rates will be analyzed using a negative binomial regression including the treatment, baseline HbA1c, subgroup, 2-way interaction of subgroup and treatment as covariates, and log (exposure in year) as the offset.

The interaction effects will be evaluated using a significance level of 0.1, unadjusted. If the interaction effect is significant ($p < 0.1$), separate analysis without the terms related with the subgroup will be performed for each subpopulation.

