2.3.1. Protocol Risk Mitigation Features

Methods to minimize potential risks are relevant for participants assigned to LY3209590 Algorithm 1 and insulin degludec treatment groups. These include

- Thorough training on the protocol design elements and inclusion/exclusion criteria; use of an electronic diary (eDiary), a web-interface and reporting system along with availability of associated instruction manuals and reference documents.
- Careful data validation: After patient-reported data has been entered and synced remotely to the central web server, the investigator is able to view the data through the web portal and generate summary reports. An important feature of the study requires careful review of the reported information with the patient and verification of its accuracy at each study visit.
- Email notification to investigator any time the patient reports a potential severe episode of hypoglycemia (requiring assistance due to neurological impairment) in the eDiary.
- Specific criteria for fasting or persistent hyperglycemia are described protocol Section 6.1.2.3.

Importantly, in both treatment groups, the final dosing decisions remain subject to clinical judgement of the investigator. Decisions to override an algorithm-recommended dose are documented in the electronic case report form (eCRF) for Algorithm 1 and insulin degludec.

3. Objectives and Endpoints

Objectives	Endpoints
Primary	

 To investigate the efficacy of LY3209590 compared with insulin degludec in study participants with T2DM 	
 HbA1c change from baseline to Week 26
Secondary	
Efficacy	

 To investigate the efficacy of LY3209590 compared with insulin degludec in study participants with T2DM 	
 HbA1c change from baseline to Week 12 Fasting glucose change from baseline to Weeks 12 and 26
Safety	

 To investigate the safety of LY3209590 compared with insulin degludec in study participants with T2DM 	
 Incidence and rate of hypoglycemia events during the treatment period Incidence of treatment-emergent serious adverse events
Pharmacokinetics	

 To characterize the PK of LY3209590 and potential intrinsic and extrinsic factors in study participants with T2DM 	
 Steady state AUC at Week 26

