5.10.3.2. Hypoglycemia Events

According to the 2020 American Diabetes Association standard of medical care in diabetes, there are two levels of hypoglycemia defined by glucose concentration:

- Level 1: glucose <70 mg/dL (3.9 mmol/L) and glucose \geq 54 mg/dL (3.0 mmol/L)
- Level 2: glucose <54 mg/dL (3.0 mmol/L)

With the above glucose reading requirement for Level 1 and 2 hypoglycemia, the following type of hypoglycemia events will be derived: documented hypoglycemia, documented nocturnal hypoglycemia (occurs between bedtime and waking), and documented non-nocturnal hypoglycemia (occurs between waking and bedtime).

Per the study protocol, severe hypoglycemia is reported as a serious AE. Severe hypoglycemia is defined in the protocol and is consistent with the ADA definition, but also requires investigator confirmation of neurological impairment. The 2020 American Diabetes Association standard of medical care in diabetes also classified severe hypoglycemia as Level 3 hypoglycemia. During a severe hypoglycemia episode, the participant has an altered mental status and cannot assist in his/her own care, may be semiconscious or unconscious, or experience coma with or without seizures, and may require assistance of another person to actively administer carbohydrate, glucagon, or other resuscitative actions. This information will be collected in the patient eDiary and the severe hypoglycemia will be listed.

[Table BDCL.1](#) provides the summary of statistical method for hypoglycemia event related analysis. Additionally, severe hypoglycemia events will be listed. The severe hypoglycemia reported as spontaneous AE in the eCRF will also be summarized by MedDRA PT. The Level 2 and Level 3 are usually considered as clinically significant hypoglycemia. Therefore, the analysis on a composite of Level 2 and Level 3 (denoted as Level 2/3) hypoglycemia will also be conducted.

Table BDCL.1. Hypoglycemia Event Related Analyses

Endpoint	Time Point*	Statistical Method
Rate of hypoglycemia events for Level 1 and Level 2/3 
 • Documented • Nocturnal • Non-Nocturnal 	0-12, 0-26, 12-26 weeks, post-treatment period (up to Visit 801)*	Exposure-adjusted rate per year / 100 years (calculated by total number of events divided by total exposure for individual patients) will be provided and the empirical method (see Appendix 1 for details) will be used for treatment comparison.

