Incidence of hypoglycemia events for Level 1 and Level 2/3 
 • Documented • Nocturnal • Non-Nocturnal 	0-12, 0-26, 12-26 weeks, post-treatment period (up to Visit 801)*	Logistic regression will include treatment, baseline HbA1c in the model. Note that the logistic regression will be conducted when ≥ 10 patients with this event.

 • Proportion of patients with HbA1c <7% without documented nocturnal hypoglycemia event (Level 1 and Level 2) • Proportion of patients with HbA1c $\leq 6.5\%$ without documented nocturnal hypoglycemia event (Level 1 and Level 2) 	0-26 weeks	Logistic regression will include treatment, country, DPPIV [yes/no], SGLT2 [yes/no], baseline BMI [<30 , ≥ 30], and baseline HbA1c in the model.

Abbreviations: BMI = body mass index; HbA1c = hemoglobin A1c; Level 2/3= Level 2 and Level 3 composite.
Note: The hypoglycemia rate per year during defined period is calculated by the number of hypoglycemia within the period/number of days patient at risk within the period*365.25 days. The hypoglycemia incidence during defined period indicates if the patient has at least 1 hypoglycemia events within the period (Yes/No). The baseline hypoglycemia rate is the rate calculated between Visit 2 and Visit 3.

*Analyses for endpoint during post-treatment period (up to Visit 801) will include all of the data after study drug discontinued on Safety population; analyses for endpoints during other time points will include all data before study drug discontinued on Safety population.

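### SAP 5.12 limits the only subgroup hypoglycemia outcome to readings of 54 to <70 mg/dL, so the clinically significant events enter no subgroup analysis

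*SAP*

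**What the plan says.** The protocol's secondary safety endpoint (Section 3) is "Incidence and rate of hypoglycemia events during the treatment period". Protocol 9.4.6.3 asks for analysis by the ADA classification.

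SAP 5.10.3.2 turns this into levels. The first is "Level 1: glucose <70 mg/dL (3.9 mmol/L) and glucose" at or above 54 mg/dL, a band closed at both ends. The second is "Level 2: glucose <54 mg/dL (3.0 mmol/L"). Level 3 is severe hypoglycemia. The section states that "The Level 2 and Level 3 are usually considered as clinically significant hypoglycemia", and for that reason "the analysis on a composite of Level 2 and Level 3 (denoted as Level 2/3) hypoglycemia will also be conducted". This is the only pooled rate or incidence class.

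Table BDCL.1 has one row for "Rate of hypoglycemia events for Level 1 and Level 2/3" and one for "Incidence of hypoglycemia events for Level 1 and Level 2/3". Each is split into documented, nocturnal and non-nocturnal events.

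SAP 5.12 names one hypoglycemia outcome for all its subgroups, "Documented hypoglycemia, non-nocturnal, and nocturnal hypoglycemia rates", over 0-26 weeks and only in the 54 to <70 mg/dL band. It fits a negative binomial model with a treatment-by-subgroup interaction, tested at an unadjusted 0.1. Separate subgroup analyses follow if p<0.1. The SAP revision history repeats the same band, so it is not a slip in one place.

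**The concern.** A count in a band closed at both ends does not always rise with risk. An event at 60 mg/dL counts and an event at 50 mg/dL does not. If events in one treatment-by-subgroup cell become deeper without becoming more frequent, the band rate in that cell falls.

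In SAP 5.12 nothing else would show this. No Level 2, Level 3 or cumulative <70 mg/dL outcome stands beside the band. The section can therefore miss a subgroup in which the weekly insulin produces more clinically significant events, or report that subgroup as doing better. Protocol 2.2 names a higher risk or longer duration of hypoglycemia as the theoretical downside of such a long-acting product, so this is a question the subgroup tables should be able to address.

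**Working it through.** **Inputs.** The documents give no hypoglycemia rates, and their only power statement concerns HbA1c, so there is no planned figure to reproduce. All rates and shares below are assumptions. Let R be the true rate ratio (LY3209590 to degludec) for all events <70 mg/dL, and let s1 and s0 be the shares of those events below 54 mg/dL on LY3209590 and degludec.

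**Formulas.**
- Band (Level 1) rate ratio = R × (1 − s1)/(1 − s0)
- Ratio below 54 mg/dL = R × s1/s0

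**Range of results with s0 = 10%.**

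| R | s1 | Band ratio | Ratio <54 | Ratio <70 |
|---|---|---|---|---|
| 1.0 | 20% | 0.80/0.90 = 0.89 | 2.0 | 1.0 |
| 1.0 | 30% | 0.70/0.90 = 0.78 | 3.0 | 1.0 |
| 1.0 | 40% | 0.60/0.90 = 0.67 | 4.0 | 1.0 |
| 1.1 | 40% | 1.1 × 0.60/0.90 = 0.73 | 4.4 | 1.1 |

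**As an interaction, which is what 5.12 tests.** Suppose that in subgroup A nothing differs (R = 1, both shares 10%), so every ratio is 1.00.
- *Reversed sign.* In subgroup B, R = 1 and s1 = 30%. The band ratio is 0.78, so B appears to do better on LY3209590 than A. Below 54 mg/dL its ratio is 3.0.
- *Missed.* In subgroup B, s1 = 30% and R = 0.90/0.70 = 1.29. The band ratio is 1.29 × 0.70/0.90 = 1.00, the same as in A, so there is no interaction to find. Below 54 mg/dL the ratio is 1.29 × 3 = 3.9, and the total is up 29%.

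**Why the main analysis is better placed.** The SAP Appendix 1 method was simulated with 125 per arm, 0.5 years, 2 events per patient-year, gamma variance 0.5 to 2, R = 1, s0 = 10%, a 90% CI and 3,000 runs per setting. Level 2/3 was represented by events <54 mg/dL.
- Band CI wholly below 1: 31-45% of runs at s1 = 30%, and 53-77% at s1 = 40%.
- CI for all events <70 wholly below 1: 5-6% of runs.
- Level 2/3 comparison showing the excess: 93% of runs or more.

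Table BDCL.1 has that last comparison and SAP 5.12 does not. The simulation covers the whole-arm comparison, not the negative binomial interaction model of 5.12.

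**What Table BDCL.1 does and does not yield.** The two rates share an exposure denominator, so a crude overall rate is nearly their sum; a severe event with a reading in the band could be counted twice. Overall incidence cannot be obtained by adding, because one patient may have both classes. Nor can a confidence interval for the pooled rate ratio, because Appendix 1 uses the variance of per-patient counts and the two counts are correlated.

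**The case against.** The strongest reply has four parts.

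1. *The levels are those the protocol asks for.* A reader might infer that the secondary endpoint is breached or left unestimated. The documents do not support that. Protocol 9.4.6.3 requires the ADA classification, the SAP applies it, and no single all-events estimate is promised. This stands.

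2. *The main table already guards against a misleading result.* A reader might infer that the whole diary analysis can present deeper events as benefit. It would normally not, because Level 2/3 is compared beside Level 1 over the same periods and splits. This stands, and it confines the main risk to SAP 5.12. Other partial cover exists. The HbA1c-target rows of Table BDCL.1 name nocturnal Level 1 and Level 2 events together, severe events are listed, and SAP 5.11.2.1 plans a cumulative <70 mg/dL class for sensor episodes. None of these gives a diary rate by subgroup.

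3. *Lower glucose usually raises the band too.* Events enter at 70 as well as leaving at 54. For normal glucose with an assumed SD of 25, moving the mean from 110 to 100 mg/dL takes the band from 4.2% to 8.2% and readings <54 from 1.3% to 3.3%, the same direction. So it would be wrong to say that lower readings generally reduce the band rate. Reversal needs a similar total with a larger share below 54, and a subgroup effect needs that shift to differ between subgroups. This stands as a limit on likelihood. It does not explain leaving the events below 54 out.

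4. *A pooled rate does not expose the excess either.* In the R = 1 examples it is 1.0 while the ratio below 54 is 2 to 4. This stands, and it is why Level 2/3 must be shown beside any pooled outcome.

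**Conclusion.** The point holds for SAP 5.12. The subgroup hypoglycemia analyses exclude every Level 2 and Level 3 event, and no companion outcome would show a subgroup difference among them. That exclusion is plain from the text. How far it could mislead rests on assumed shares: with equal totals and 10% on degludec against 20-40% on LY3209590 below 54 mg/dL, the band ratio is 0.89 to 0.67 while the ratio below 54 is 2 to 4. These figures show what is possible. They do not predict the trial's result.

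For the main diary analysis the gap is narrower: no pooled incidence and no pooled treatment comparison with a CI for all events <70 mg/dL. This is an inexpensive improvement to unadjusted subgroup analyses and a supplement to the main table.

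**What to change.** - **SAP 5.12:** replace the band with all documented events <70 mg/dL or severe (Levels 1, 2 and 3 combined, each event counted once), split into documented, nocturnal and non-nocturnal. An event stays in this count however low its reading.
- **SAP 5.12:** tabulate Level 2/3 by treatment and subgroup beside it, descriptively where counts are too small to model.
- **Table BDCL.1:** add the combined class to the rate and incidence rows as a supplement, keeping Level 1 and Level 2/3.
- **Definition:** state how a reading of exactly 70 mg/dL is classed in the analysis. Protocol 6.1.2.2 and 8.3.7.1 use ≤70 mg/dL; SAP 5.10.3.2 uses <70.

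The cost is SAP wording and a few rows from data already derived. The combined outcome will be dominated by Level 1 events, and Level 2/3 subgroup counts will probably be small. With the assumed 2 events per patient-year and 10% below 54, half of one arm (62.5 patients for 0.5 years) gives 62.5 × 0.5 × 2 × 0.10 = about 6 events.
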